1.0 Introduction

The planned interim analysis of the study was conducted, and the study was stopped at the recommendation of the Data Safety Monitoring Board because of the demonstration of efficacy based on the primary endpoint. The interim analysis was conducted, as planned, based on data through the date of occurrence of the 28th Clinical Adjudication Committee (CAC)-adjudicated catheter-related blood stream infection (CRBSI) (03 December 2017). While the data for the interim analysis were being source verified and cleaned, the study continued and more data were accrued. The purpose of this addendum to the Statistical Analysis Plan (SAP) is to describe (1) planned efficacy analyses of the three efficacy endpoints based on all of the efficacy data through the last patient's last visit (LPLV), (2) planned safety analyses of all of the safety data through the LPLV, and (3) other analyses.

1.1 Efficacy Analyses

Primary Endpoint

The primary endpoint is catheter-related blood stream infection (CRBSI), defined as one positive blood culture (other than for coagulase negative *Staphylococcus*, which requires a confirmatory culture) from:

1. a peripheral site or blood line sample or
2. either the arterial or venous catheter hub (or the venous or arterial dialysis circuit blood lines if on dialysis)

in a patient with no other apparent source of bloodstream infection other than the hemodialysis catheter, as assessed by the Clinical Adjudication Committee (CAC).

The primary analysis of the primary endpoint was performed at the interim analysis, and it resulted in a positive outcome and the stopping of the study. This analysis of this endpoint represents the final formal analysis for this endpoint. Nevertheless, in order to summarize all of the available information on this endpoint, the analysis of the primary endpoint will be repeated using all of the data through the LPLV. The p-value from this analysis will be reported to provide a measure of the strength of evidence of efficacy from the study but it will not represent a second test of the null hypothesis for this endpoint. As for the interim analysis, the analysis of the primary endpoint based on all of the data through the LPLV will be conducted based on the Full Analysis Population using the Kaplan-Meier method. The time until CRBSI will be calculated as the number of days post randomization until the occurrence of a CAC-adjudicated CRBSI. A patient will be considered to have a CRBSI event if there is a CAC-determined CRBSI. If there is no such CRBSI, the patient will be censored at the earliest of the following dates:

1. Date of catheter removal, if any
2. Date of study completion, if any
3. Date of last study drug dose plus 3 days

Three days was added to the date of last study drug dose because the study drug would be withdrawn at the next dialysis session, which would typically be about three days later.

In this analysis of the primary endpoint, cases adjudicated as indeterminate by the CAC will not be considered to be CRBSI cases. A sensitivity analysis will be performed in which cases adjudicated as

indeterminate will be considered to be CRBSI cases. Subgroup analyses of the primary analysis of the primary endpoint will be conducted as described in the Statistical Analysis Plan. These analyses will be performed based (1) on all of the efficacy data through the data cutoff date for the interim analysis and also (2) on all of the efficacy data through the LPLV.

Secondary Endpoints

The secondary endpoints are as follows:

- Catheter Removal: Defined as catheter removal for any reason during the follow-up period of the trial.
- Loss of Catheter Patency: Defined as required use of a tissue plasminogen activating factor (tPA) or removal of the catheter because of dysfunction during the follow-up period of the trial.

Analyses of these endpoints were conducted and provided to the Data Safety Monitoring Board at the time of the interim analysis. Unlike the primary endpoint, however, the primary analyses of these endpoints will be based on data through the LPLV.

Time until catheter removal for any reason and time to loss of catheter patency will be analyzed based on the Full Analysis Population using the Kaplan-Meier method as for the primary endpoint.

A patient will be considered to have had loss of catheter patency if either of the following conditions are met:

1. If the reason for study completion is specified as “Catheter Removal (not due to CRBSI)” and the reason (for catheter removal) is indicated as being “Catheter Malfunction/Dysfunction – Loss of patency” or
2. If the Reported Name of Drug Med or Therapy (Preferred) is “Alteplase” and the item “For tPA usage, if the usage was directly related to a loss of patency” is indicated as “Yes”.

The time of the event will be the number of days between randomization and the event. (If both of the above conditions are met, the date of occurrence of the earlier condition will be used.) If there is no such loss of catheter patency, the patient will be censored at the earliest of the following dates:

1. Date of catheter removal, if any
2. Date of study completion, if any
3. Date of last study drug dose plus 3 days

A patient will be considered to have had a catheter removal if there is a date of catheter removal. If a patient does not have a date of catheter removal, the patient will be considered censored at the earliest of the following dates:

1. Date of study completion, if any
2. Date of last study drug dose plus 3 days

The time to the event will be the number of days between randomization and the event.

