1.5 Sample Size

This trial has been designed to achieve 80% power for the comparison between treatment arms subject to the following specifications: testing will be conducted at a 2-sided overall 5% alpha level using the log-rank test, Neutrolin is associated with a 55% reduction in the risk of CRBSI relative to the control arm, a 1 to 1 ratio will be used for the allocation of subjects to treatment arms, and one interim analysis will be performed at the midpoint of the trial with adjustment of the alpha level using the method of Pocock. Fifty-six CRBSI events in total will be needed to achieve the desired power. The interim analysis will be conducted based on the first 28 CRBSIs. The total sample size is expected to be approximately 900 subjects.

2 Statistical Methods

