2.4 Statistical Assessment of the Trial Objectives

2.4.1 Primary Endpoint Analysis

The primary analysis will be conducted using a log-rank test for the time to CRBSI at an overall 2-sided 5% alpha level. The null hypothesis is that there is no difference in the hazard rates of CRBSI over time between the two treatments. The time until CRBSI will be calculated as the number of days post randomization until the occurrence of a CAC-adjudicated CRBSI or the subject is censored. Subjects without a CRBSI will be treated as censored in this analysis if the catheter is removed for reasons other than CRBSI (e.g., catheter removed because no longer required) or follow-up is completed in the absence of CRBSI. Because an interim analysis for efficacy will be performed, the method of Pocock will be used to control the overall alpha level. Therefore, the nominal significance level at the interim and final statistical analyses for the primary efficacy endpoint will be 0.0294.

The primary analysis will be based upon the Full Analysis Population. While testing will be based upon the log-rank test, the estimated treatment effect will be the difference between treatment groups in the incidence rate of CRBSI, calculated as the number of subjects with a CRBSI divided by the number of catheter-days of follow-up over subjects (follow-up will be based upon the same time as used for the log-rank test). The rates will be presented as the event rates per 1000 catheter-days with a 95% confidence interval for the purpose of comparison of rates between the treatments. This confidence interval will be derived assuming that the number of catheter-days until CRBSI follows an exponential distribution.

In the primary analysis of the primary endpoint, cases considered to be indeterminate by the CAC will be excluded. A sensitivity analysis will be performed in which cases considered to be indeterminate will be treated as CRBSI events.

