2.4.2 Secondary Endpoint Analyses

Time until catheter removal for any reason and time to loss of catheter patency will be analyzed using similar methods as for the primary analysis in the Full Analysis Population. Loss of catheter patency is defined as required use of a tissue plasminogen activating factor (tPA) or removal of the catheter due to dysfunction. For these endpoints, subjects will be considered censored as of their final clinical assessment if the event of interest is not observed. Otherwise, the event time will be the number of catheter-days between randomization and the event. The fixed sequence testing procedure will be used for the comparison of the two treatments with respect to the efficacy endpoints. Therefore, the analysis comparing the two treatments for catheter removal for any reason will be formally conducted only if the analysis for the primary effectiveness endpoint yields a statistically significant result favoring Neutrolin®, and the analysis comparing the two treatments for loss of patency will be formally conducted only if the analysis for catheter loss for any reason also yields a statistically significant result favoring Neutrolin®.

In addition to basic descriptive statistics, the rates per 1000 catheter-days of follow-up will be presented for both endpoints. Also, the reason for catheter loss will be summarized by treatment group.

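### Must the plan state a significance level for catheter removal and loss of patency, now that they are tested on data through the last patient's last visit?

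*SAP*

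**What the plan says.** SAP 2.4.1 sets an overall two-sided 5% level for the primary log-rank test. Because an efficacy look is planned, it then applies Pocock's method: "the nominal significance level at the interim and final statistical analyses for the primary efficacy endpoint will be 0.0294". Protocol 9.7 says the same. SAP 1.5 states the design level: "testing will be conducted at a 2-sided overall 5% alpha level using the log-rank test". The protocol synopsis gives two-sided 5% for the primary test and does not mention 0.0294.

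For the secondary endpoints, SAP 2.4.2 says that they "will be analyzed using similar methods as for the primary analysis in the Full Analysis Population". Catheter removal is formally tested only after a significant primary result in Neutrolin's favor. Loss of patency is tested only if "the analysis for catheter loss for any reason also yields a statistically significant result favoring" Neutrolin. SAP 2.4.2, SAP 3.7.3 and protocol 9.7.1 give no numeric level for either.

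Section 1.1 of the SAP addendum (November 2018) makes the interim result the final formal analysis of the primary endpoint. Of the LPLV repeat it says that "it will not represent a second test of the null hypothesis for this endpoint". On the secondaries it records: "Analyses of these endpoints were conducted and provided to the Data Safety Monitoring Board at the time of the interim analysis". It then continues: "Unlike the primary endpoint, however, the primary analyses of these endpoints will be based on data through the LPLV". It adds that they "will be analyzed based on the Full Analysis Population using the Kaplan-Meier method as for the primary endpoint". It gives no level and does not repeat the testing order.

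**The concern.** Two readings can be drawn from the text. The phrase about similar methods in SAP 2.4.2 could carry 0.0294 over to the secondaries. The overall 5% level, with one test per secondary, gives 0.05. The 95% confidence intervals do not decide between them, because the primary is tested at 0.0294 and also gets 95% intervals.

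Two claims would hang on this. A catheter-removal p-value between 0.0294 and 0.05 is significant on one reading and not on the other, and that verdict decides whether loss of patency is formally tested at all. The addendum also postdates the interim secondary analyses given to the DSMB. It says outright that the extra primary analysis is not a second test, but has no matching sentence for the interim secondary analyses.

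**Working it through.** **1. The plan's own figure.** For two looks at information 0.5 and 1, the correlation of the two statistics is √0.5 = 0.707. Solving P(|Z₁| > c or |Z₂| > c) = 0.05 gives c = 2.178, and 2[1 − Φ(2.178)] = 0.0294. The stated level is reproduced. It is the cost of two tests of one hypothesis.

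**2. How many tests each secondary gets.** The addendum names one primary analysis per secondary, on LPLV data. If the interim and LPLV analyses both counted as tests, two equally spaced looks at 0.05 would give 8.3% two-sided error, and two at 0.0294 would give 5.0%. With one designated analysis, that cost does not arise.

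**3. How often the choice of level changes the verdict.** Let Z be normal with mean μ = 1.960 + Φ⁻¹(power at 0.05). The gap is P(1.960 < Z < 2.178). At 80% power, μ = 1.960 + 0.842 = 2.802, so the gap is Φ(2.178 − 2.802) − Φ(1.960 − 2.802) = 0.266 − 0.200 = 0.066.

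| Power at 0.05 | Power at 0.0294 | Gap |
|---|---|---|
| 50% | 41.4% | 8.6% |
| 80% | 73.4% | 6.6% |
| 90% | 85.6% | 4.4% |

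The maximum is 8.7%, at μ = 2.069. With no true effect, the gap in Neutrolin's favor is 0.025 − 0.0147 = 0.0103. The power values are assumptions, since the plan powers only the primary.

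**4. Error of one LPLV test at 0.05 after a positive primary.** The model uses a primary boundary of 2.178 at information 0.5 and 1. A null secondary is tested once: at LPLV fraction f if the primary stops at the interim, otherwise at full information. The correlation ρ between the two statistics, and f, are assumed. Total two-sided error is at most 5.0% (at most 2.9% at level 0.0294). Simulated false benefit, maximized over the primary effect, against a nominal 2.5%:

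| f | ρ = 0.3 | ρ = 0.5 | ρ = 0.8 | ρ = 1 |
|---|---|---|---|---|
| 0.50 | 2.60% | 2.73% | 3.14% | 3.99% |
| 0.60 | 2.57% | 2.66% | 2.93% | 3.31% |
| 0.75 | 2.52% | 2.57% | 2.72% | 2.91% |
| 0.90 | 2.51% | 2.52% | 2.57% | 2.65% |

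At level 0.0294 the largest value was 2.51% (ρ = 1, f = 0.50). The row f = 0.50 is a limit: the addendum introduction says more data accrued after the interim cutoff. The column ρ = 1 is also a limit, because removal for any reason includes malfunction and catheters no longer needed.

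**The case for a change.** The best case for a change is that the plan states only one nominal level, 0.0294, and a decision rule should be written down rather than inferred, above all in an addendum dated after interim secondary results existed. For subgroups, safety and other data the addendum refers back to the SAP; for the secondaries it does not. The remedy is one sentence and no new analysis. Nor is 0.05 free of cost: false benefit exceeds 2.5% when the secondary is correlated with the primary and LPLV adds little information.

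Part of this stands. No numeric level is given, and 0.05 cannot be called exact for benefit claims on inputs the documents do not supply.

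The rest is weaker. The two readings are not equally supported: 0.0294 is introduced because of the interim efficacy look and is confined in words to the primary endpoint. In the protocol synopsis and protocol 9.7.1, the similar-methods phrase concerns estimating rates. A fixed sequence ordinarily passes the full level to each step. The addendum supplements the SAP without withdrawing 2.4.2, and lists the secondaries in the same order. By naming LPLV as the primary analysis for the secondaries, in contrast to the primary endpoint, it already makes their interim analyses non-primary. Order, conditions, population, test, data cut and censoring are all stated; one number is not.

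**Conclusion.** No change to the plan follows. The level is missing, but an analyst following the documents would test each secondary once, at LPLV, in the SAP 2.4.2 order, at two-sided 0.05. That keeps total two-sided error at or below 5.0%. A stated level would record this reading; it would not correct a wrong rule or supply a better method. SAP 3.1 has p-values reported to four decimals, so a reader can set a catheter-removal result against either level.

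The size is modest. The verdict depends on the level with probability 4.4% to 8.7% for power between 50% and 90% at 0.05. False benefit at 0.05, with f between 0.55 and 0.90, is 2.5% to 2.7% at correlation 0.5 and 2.6% to 3.6% at correlation 1. These ranges assume that the secondary's information fraction tracks the primary's and that the interim falls at half of planned information. Correlation and LPLV information are not in the documents, so the excess over 2.5% is a possibility with a range, not a finding.

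### The SAP addendum stops the clock at last dose + 3 days for event-free patients only, so later events count while comparable event-free time off drug is dropped

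*SAP*

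**What the plan says.** The SAP addendum, 1.1 Efficacy Analyses, first decides whether a patient had the event and only then gives a censoring date to those who did not.

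- **Catheter removal.** The endpoint is "Defined as catheter removal for any reason during the follow-up period of the trial", and the counting rule is "A patient will be considered to have had a catheter removal if there is a date of catheter removal". Then: "If a patient does not have a date of catheter removal, the patient will be considered censored at the earliest of the following dates". Those dates are study completion and "Date of last study drug dose plus 3 days".
- **Loss of patency.** It counts on a dysfunction removal given as the reason for study completion, or on any alteplase record marked as directly related to loss of patency. Then: "If there is no such loss of catheter patency, the patient will be censored at the earliest of the following dates". The list is catheter removal, study completion, and last dose plus 3 days.
- **CRBSI through the last patient's last visit (LPLV).** "A patient will be considered to have a CRBSI event if there is a CAC-determined CRBSI". Otherwise the same three-date list applies.

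The dose-based date is in every censoring list and in no event rule. For the two secondary endpoints this is the main analysis: "Unlike the primary endpoint, however, the primary analyses of these endpoints will be based on data through the LPLV".

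The SAP itself has no dose-based cap. For the secondary endpoints, 2.4.2 says "subjects will be considered censored as of their final clinical assessment if the event of interest is not observed", and 3.7.3 repeats it. For CRBSI, 2.4.1 and 2.6 censor at catheter removal or end of follow-up.

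**The concern.** Take two patients who both stop study drug on day 100 with the catheter still in place. One has it removed on day 120: she is an event at day 120, with 120 days at risk. The other keeps it: she is censored at day 103. Time at risk between days 103 and 120 is credited only to the patient who goes on to have the event. Censoring then depends on the later outcome, which the log-rank test, Kaplan-Meier estimate and person-time rate all assume it does not.

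Such late events can be recorded. Protocol 7.1.7 (early withdrawal visit) and 7.1.6 (final safety visit, 28 + 7 days after the last dose is removed) both assess clinical endpoint events, and 7.1.6 also records thrombolytic use.

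At stake are the reported rates per 1,000 catheter-days and, if the arms differ in stopping drug with the catheter in place, the hazard ratios and fixed-sequence tests for catheter removal and loss of patency. The LPLV CRBSI analysis is not a formal test, so there only the reported figures are affected. The addendum is dated November 2018, after the efficacy stop. It explains why the margin is 3 days, but not why events are exempt or why the SAP's rule was replaced.

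**Working it through.** **The plan's own figure.** No number in the plan is attached to this rule. The design figure reproduces and is unaffected: two-look Pocock boundary 2.178, nominal level 0.0294; hazard ratio 0.45 needs 54.7 events for 80% power, and the stated 56 give 81.0%.

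**Direction of the rate error.** Against full follow-up the numerator is the same and the denominator is smaller, so the rate is too high whenever event-free patients have follow-up after the cap.

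**Inputs.** From the documents: the 3-day cap, the 28-day off-drug window, about 450 patients per arm. Assumed, because the documents give no values: removal hazard λ = 0.005 per day in both arms (no drug effect), drug-stopping hazard *d*, and administrative follow-up uniform on 60 to 700 days.

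**Hand calculation, catheter removal.** Per patient, with k = λ + d and off-drug follow-up only for those who stop drug early:

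- S = (e^(−60k) − e^(−700k)) / (640k); on-drug days T = (1 − S)/k; proportion stopping in place p = dT
- removals on drug = λT; in the first 3 days off drug = p(1 − e^(−3λ))
- late removals, after the cap to day 28 = p·e^(−3λ)·(1 − e^(−25λ))

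| | Heparin, d = 1/400 | Neutrolin, d = 1/800 |
|---|---|---|
| S | 0.1317 | 0.1687 |
| T (days) | 115.77 | 133.01 |
| p | 0.289 | 0.166 |
| Removals on drug | 0.5788 | 0.6651 |
| Removals (days at risk), first 3 days off | 0.0043 (0.86) | 0.0025 (0.50) |
| Late removals | 0.0335 | 0.0192 |
| Post-cap days kept by the addendum (event patients only) | 0.41 | 0.24 |
| Post-cap days, everyone | 6.70 | 3.85 |

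Addendum rate, heparin: (0.5788 + 0.0043 + 0.0335)/(115.77 + 0.86 + 0.41) = 0.6166/117.04 = 5.27 per 1,000 days. With all post-cap time: 0.6166/(115.77 + 0.86 + 6.70) = 5.00. With events and time both cut at the cap: 0.5831/116.63 = 5.00.

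Addendum rate, Neutrolin: 0.6868/133.75 = 5.135. The ratio is 5.135/5.269 = 0.975, where the truth and both symmetric rules give 1.00.

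**Simulation, same inputs** (450 per arm, log-rank at an assumed two-sided 0.05, 1,500 to 3,000 replicates). Cells are hazard ratio / rejection rate; a dash means not reported.

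| Stopping, heparin vs Neutrolin | Addendum | Both capped | Both to day 28 |
|---|---|---|---|
| 1/600 vs 1/600 | 1.00 / 5.4% | – | – |
| 1/1000 vs 1/1500 | 0.995 | 1.002 | – |
| 1/400 vs 1/800 | 0.973 / 6.7% | 0.998 / 5.0% | 0.999 / 4.8% |
| 1/400 vs 1/800, removal 3 times likelier off drug | 0.933 / 13.1% | 0.993 / 5.0% | 0.952 / 8.9% |

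In the first row the removal rate is 5.17 against 5.00. In the last row, part of the 8.9% is a real off-drug difference. Reversing the imbalance gives addendum hazard ratios of 1.024, and 1.072 with the threefold hazard.

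**Other endpoints, same approach.**

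- tPA limb (2 per 1,000 days): equal stopping, 2.08 against 2.01; 1/400 vs 1/800, hazard ratio 0.976 against 1.004 capped and 1.002 full.
- CRBSI (0.6 per 1,000 days, equal stopping): rate overstated by about 1%, 2%, 4% and 7% when 7%, 13%, 20% and 33% stop in place. The hazard ratio is 0.446 under all three rules when the truth is 0.45.

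**Second simulation, different assumptions** (400 per arm, 2 to 6 events per 1,000 days, stopping 1 vs 3 per 1,000 days, no true difference): rate ratio 1.04 to 1.06 and rejection 5.9% to 8.9% under the addendum; 1.00 to 1.01 and 4.4% to 5.4% under either symmetric rule. If every patient also has 28 off-drug days at study close, equal stopping raises both arms' rates by about 7% to 10% (for example 2.00 to 2.21), with the ratio at about 1.00.

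**The case against.** The strongest reply accepts the wording and disputes how much it matters.

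- **Follow-up period.** Secondary events are limited to the trial's follow-up period. The protocol synopsis ends follow-up at study withdrawal, and Protocol 5.3.2 describes the 28 days after stopping treatment as safety monitoring for patients who agree. On that reading many late events would not count. But 7.1.6 and 7.1.7 collect endpoint events in that window, and SAP 1.2 does not list withdrawal as an end of follow-up. The text is ambiguous, and the limit is not tied to dosing in any case.
- **Window length.** The effect shrinks with a shorter window. At 1/400 vs 1/800, a 14-day window gives a hazard ratio of 0.984 and a 7-day window 0.995. This stands as a limit on size.
- **Imbalance.** Bias in the comparison needs a marked between-arm difference in stopping, which nothing in the documents suggests. The 13.1% needs that difference, a threefold off-drug hazard and the full 28 days together. This also stands.
- **Test level.** The 0.05 used for the secondary tests is an assumption; the plan gives 0.0294 for the primary endpoint only.
- **Narrow reach.** The removal limb of loss of patency is tied to the reason for study completion, so the exposure there is mainly tPA use.
- **Estimand choice.** An on-treatment window is a legitimate choice. It must then bind events as well as censoring, which the addendum does not do.

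**Conclusion.** The concern holds. As written, the addendum makes time at risk depend on whether an event later occurs, for all three endpoints, and departs from the SAP's censoring without giving a reason. This is an error in a stated rule, not missing detail.

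The certain consequence is rates that are too high whenever event-free patients have off-drug follow-up: about 1% to 14% across the scenarios tried. The comparison between arms is unbiased if stopping is equal and negligibly affected under mild imbalance. Under strong imbalance it shifts by roughly 2% to 7% in the hazard or rate ratio, in either direction. All of these sizes rest on assumed stopping, event and follow-up rates, and most also on a full 28-day off-drug window. The documents give neither stopping rates nor late-event counts, so direction and actual size are unknown.

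The point matters most for catheter removal and for the tPA limb of loss of patency. It should be fixed, but nothing here shows that the trial's main conclusion is affected. Whether the interim CRBSI test used the cap is not stated: the addendum's comparison with the interim covers only the population and the Kaplan-Meier method.

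**What to change.** 1. Apply one time window to both events and censoring, for all three endpoints.
2. Make the SAP's pre-specified censoring the main analysis: 2.4.2 for catheter removal and loss of patency, 2.4.1 and 2.6 for CRBSI. Define the final clinical assessment date, which the SAP leaves open, and say whether the 28-day off-drug period belongs to efficacy follow-up.
3. Keep last dose plus 3 days as an on-treatment sensitivity analysis in which events after that date are also not counted.
4. Report by arm the number of patients who stopped study drug with the catheter in place and the number of events after last dose plus 3 days. If both are small, the matter is closed.
5. State which censoring rule the interim CRBSI analysis used.

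The cost is one reprogrammed censoring date per endpoint, one sensitivity run and one count table. No new data are needed.
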